6.4.2 Subject Enrollment

Prior to enrollment in the study, subjects will be evaluated to determine eligibility. The subject's willingness and ability to meet the follow-up requirements will be determined. If the subject desires to participate in the study, written informed consent will be obtained prior to performance of any study-specific examinations (see Section 6.4.3). Each subject will be assigned a screening number and will be entered on a screening log, which will be submitted regularly to the Sponsor. After the informed consent has been signed, a unique 5-digit subject identification number which includes the 2-digit site number plus a sequential 3-digit subject number starting at 001 (e.g., 01-001) will be assigned and subject is screened for eligibility criteria and considered enrolled in the study if all eligibility criteria is met. No two subjects will have the same five-digit subject identification number. This subject identification number will identify the subject throughout the study and will be used for all source documents and CRFs. Subjects who meet the eligibility criteria and agree to participate will be scheduled for TraceIT Tissue Spacer injection and fiducial marker placement.

A subject is considered enrolled in the study after the subject meets eligibility criteria. Only subjects who undergo TraceIT Tissue spacer injection attempt (i.e., at the time the needle is inserted through the duodenum) will be included in the safety/effectiveness populations for analysis. All subjects enrolled in the study will be required to adhere to the follow-up schedule outlined in this protocol. Subjects withdrawing consent after treatment will not be required to undergo follow-up after withdrawal; however, these participants will still be considered part of the study cohort and included in the safety analysis.

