6.4.5.1 Injection

The TraceIT Tissue Spacer is to be injected between the pancreas and the duodenum by the participating study physician using a transduodenal approach and with endoscopic ultrasound (EUS) guidance as depicted in **Figure 2**.

An EUS assessment of the space between the pancreas and the duodenum before and after injection is to be performed. The following information will be collected:

- Ability to access injection site and inject TraceIT material
- Average duodenal space measurements on CT measured at 3 points along the head of the pancreas
- TraceIT Injection Procedure Duration
- Ease of Device Use
- Device malfunctions
- Adverse Events per NCI CTCAE ver. 4.0

Figure 2: TraceIT Tissue Spacer Injection into Periduodenal Space using Endoscopic Ultrasound Guidance (Rao et al, used with permission)

The subject is to be positioned in the left-lateral position and an endoscopic ultrasound (EUS) will be used to identify the duodenum and HOP interface.

Under EUS guidance, the 19 or 22G fine needle aspiration (FNA) needle will be guided through the EUS scope and into the potential space between the duodenum and pancreas. The TraceIT Tissue Spacer will be prepared per the supplied IFU. Once the needle has been confirmed to be in

the proper position, the TraceIT hydrogel will be injected in 1mL increments. This process will then be repeated as the needle is repositioned around the target region, injecting TraceIT hydrogel at each location to a total volume of up to 20 mL hydrogel (40 mL of diluted TraceIT hydrogel in a 1:1 ratio).

- Note: If the needle is inserted through the duodenum, but the TraceIT Tissue Spacer is not injected, the subject will be followed for 30 days and included in the safety analysis. No further imaging is required for these “non-injection” subjects.

Following injection of the TraceIT hydrogel, the needle is to be removed, EUS images are to be acquired and measurements obtained as described above.

The lot number of the TraceIT Tissue Spacer device(s) used, the number and timing of applications is to be recorded on the TraceIT Tissue Spacer Injection CRF.

The subject should be assessed for adverse events during the follow-up period following the TraceIT Tissue Spacer injection.

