6.4.6 RT Planning and Radiation Treatment

The technique for delivering the external beam treatment will be employed per institutional standard guidelines. Identical treatment planning studies will be performed both before (pre-TraceIT) and after (post-TraceIT) hydrogel injection in each subject. The technique and setup for these two simulation studies should be nearly identical particularly with respect to patient immobilization and respiratory motion management (i.e., active breath-hold method, forced shallow breathing with abdominal compression or real-time tracking and/or gating) and beam arrangement and angle. Planning set-up/parameters for the pre- and Post-injection RT planning will be documented within the CRF.

The initial **minimum target dose** will be 33 Gy in 5 fractions (6.6 Gy per fraction) or an equivalent biologically effective dose if >5 fractions is being delivered. The goal should be that at that the V33Gy for the PTV be at least 95%. CT simulation will be performed with immobilization when possible.

Normal tissue contours will be performed in accordance with the Upper Abdominal Normal Organ Contouring Guidelines recommended by the 2013 RTOG Consensus Panel.

Target dose constraints for OAR include:

Organs at Risk (OAR)	Dose Constraint*
Proximal duodenum, proximal stomach and small bowel	V15Gy<9cc, V20Gy<3 cc, and V35Gy<1cc A duodenal maximum dose of \leq 32 Gy should initially be attempted
Stomach	V12Gy<50% and V35Gy<1cc
Liver	V12Gy<50%
Combined Kidneys	V12Gy<75%;
Spinal Cord	V8Gy<1 cc

*or biologically equivalent dose constraints for >5 fractions

Target coverage, doses to OAR, dose conformity, mean and maximum proximal duodenal dose and dose volume histograms will be documented pre- and post-TraceIT Injection.

6.4.7 Follow-up for Non-Injection Subjects (30 days +7 days or until resolution/stabilization of an adverse event if applicable)

A “Non-Injection” Subject is a subject who was intended to be treated with TraceIT, but in whom TraceIT was unable to be injected. No further image collection is required for these subjects.

- 30 Day Visit to include:
 - Physical assessment: including sitting blood pressure, pulse, temperature and Zubrod Performance Score
 - Assessment of Intestinal Adverse Events documented using CTCAE criteria
 - Other Adverse Events per NCI CTCAE
 - Changes in concomitant medications used to treat intestinal symptoms

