7.3 Analysis Populations

7.3.1 Intent-to-Treat Population (ITT)

All enrolled (consented) subjects for whom TraceIT administration is attempted. This will be the primary analysis population for evaluation of feasibility (i.e., technical success defined as the ability to place TraceIT and create space between the duodenum and HOP).

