9.1.1 Recording and Reporting of Adverse Events

All study staff are responsible for ensuring that complete safety information has been recorded on the CRF and in source documents. All Adverse Events (AE) must be documented throughout the study. Medical assessments must be performed during each scheduled study visit and serve as the primary basis for identifying AEs. Although spontaneous or elicited medical complaints will likely constitute the majority of AEs, any non-scheduled visit to a healthcare provider or the initiation of a new medication should trigger additional questioning as to the occurrence of an AE.

All adverse events, regardless of severity or relationship to investigational device, will be collected from the time of initiation of fiducial marker placement and through the 18-month visit. Subjects who experience an adverse event related to TraceIT hydrogel will be followed until the adverse event has resolved or until the subject has stabilized and follow-up care has been transferred to the subject's primary care physician.

Any changes in a subject's condition noted prior to the procedure should be adequately assessed and included in the medical history for the subject.

Any event precipitating an intestinal acute CTCAE score of grade 2 or more must be documented as an adverse event.

To the extent possible, the event to be recorded and reported is the event **diagnosis** as opposed to event **symptoms**. Please refer to the following examples:

- Fever, chills, nausea and vomiting in the presence of a clinically diagnosed infection is to be reported as an infection only.
- Pain on urination in the presence of a clinically diagnosed urinary tract infection is to be reported as a urinary tract infection only.

Reporting Serious Adverse Events

All serious adverse events and serious adverse device effects shall be reported to the Sponsor or their representative (by fax or by phone) within 24 hours of the time the investigator learns of the event. A written report detailing the event and signed by the investigator shall be submitted to the Sponsor within 5 working days. The investigator shall notify the reviewing IRB of all serious adverse events occurring in the study according to the IRB's requirements.

Device failures or problems not associated with adverse events will be documented separately on the appropriate case report form. The product should be retained for evaluation.

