3.1.3 Statistical Methods

The proportion of TraceIT treated subjects in whom Technical Success has been achieved will be reported in ITT population, together with an exact (Clopper-Pearson) 95% confidence interval for the true proportion. This endpoint may be summarized separately also for the localized (resectable, BRPC and LAPC) subjects.

All practical monitoring and follow-up steps will be taken to ensure complete and accurate data collection. Due to the fact that subjects are undergoing therapy consistent with standard medical practices, it is anticipated that there will be minimal missing data. There will be no imputation of missing outcome data.

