4.1.5 Safety Population (SAF)

The Safety Population is defined to be all subjects for whom TraceIT administration is attempted (whether or not administration was successful). For the purposes of this study, the Safety Population is the same as the ITT Population.

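### The ITT and Safety sets start when the TraceIT needle crosses the duodenum, so an enrolled subject stopped earlier in the same endoscopy is outside the Technical Success denominator and the Safety Population percentages

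*Protocol*

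**What the plan says.** **When a subject counts.** Protocol 6.4.2 puts enrollment before the procedure: "A subject is considered enrolled in the study after the subject meets eligibility criteria". Entry to the analysis populations comes later: "Only subjects who undergo TraceIT Tissue spacer injection attempt (i.e., at the time the needle is inserted through the duodenum"). Protocol 7.3.1 defines ITT as "All enrolled (consented) subjects for whom TraceIT administration is attempted", and SAP 4.1.1 repeats it. SAP 4.1.5 states "The Safety Population is defined to be all subjects for whom TraceIT administration is attempted". Both documents then declare Safety and ITT to be the same set.

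**The primary endpoint.** SAP 3.1 calculates the Technical Success rate in ITT. SAP 3.1.3 says "The proportion of TraceIT treated subjects in whom Technical Success has been achieved will be reported in ITT population", with an exact 95% interval.

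**When data collection starts.** The Protocol Summary places fiducials and hydrogel in a single endoscopic session. Under Protocol 9.1.1, adverse events "will be collected from the time of initiation of fiducial marker placement and through the 18-month visit". The first index-procedure item in Protocol 6.4.5.1 is "Ability to access injection site and inject TraceIT material".

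**Subjects who are not injected.** The note in Protocol 6.4.5.1 keeps a non-injected subject in the safety analysis if the needle went through the duodenum. Protocol 6.4.7 is broader: a non-injection subject is "a subject who was intended to be treated with TraceIT, but in whom TraceIT was unable to be injected", with no needle condition. Table 3 schedules adverse event assessment for these subjects at the index procedure and at 30 days.

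**The concern.** Technical Success is the primary effectiveness endpoint, and reaching the injection site is part of what an early feasibility study sets out to learn. If the denominator opens only once the TraceIT needle has crossed the duodenum, a subject in whom that point is never reached is not a failure but a non-member. Such a subject cannot be a success, so leaving them out can only raise the rate or leave it unchanged.

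Safety has the same gap. Events are collected from the start of fiducial placement, but the Safety Population opens at a later step of the same session. A fiducial-phase complication that ends the procedure would be recorded for a subject who belongs to no set used for percentages. Protocol 6.5 also lets the sponsor replace subjects, so six attempted injections could still be reached with the stopped subjects outside the rate.

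**Working it through.** **Step 1. Order the events.** Enrollment at eligibility (Protocol 6.4.2), then fiducial placement and start of adverse event collection (9.1.1), then TraceIT needle through the duodenum and entry to ITT and Safety (6.4.2), then injection, then post-injection CT. That fiducials come first is inferred from the procedure's title and from the start of adverse event collection.

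Protocol 6.4.2 does not say which needle it means, and fiducials are also placed through the duodenum. But the sentence ties the needle to the TraceIT attempt, and SAP 5.1.4 records TraceIT needle insertion separately from fiducial insertion. The TraceIT needle is the natural reading.

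**Step 2. Place each enrolled subject.**

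| Where the subject stops | ITT (Technical Success) | Safety Population | Reported elsewhere |
|---|---|---|---|
| Before the index endoscopy | No | No | Disposition |
| In the endoscopy, before the TraceIT needle crosses | No | No | Event listing (Protocol 7.7); disposition (Protocol 7.5, SAP 5.1.1) |
| Needle crossed, no gel injected | Yes, as failure | Yes | 30-day follow-up |
| Gel injected, not visualized in the interface | Yes, as failure | Yes | Scheduled visits |

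Only the second row is at issue.

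**Step 3. Size.** The plan gives no design figure to reproduce: six subjects are chosen without a calculation (Protocol 7.1, SAP 3.1.2). The planned interval is Clopper-Pearson. For x successes in n, the lower limit is the 2.5% quantile of Beta(x, n − x + 1) and the upper limit is the 97.5% quantile of Beta(x + 1, n − x). At x = n the lower limit is 0.025^(1/n) and the upper is 1. At x = 0 the lower limit is 0 and the upper is 1 − 0.025^(1/n).

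The number of pre-needle stops is an assumption. Six successes among six attempts are also assumed.

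- No stop counted: 6/6 = 100%; lower limit 0.025^(1/6) = 0.541. CI 54.1 to 100.
- One stop counted: 6/7 = 85.7%; Beta(6, 2) and Beta(7, 1). CI 42.1 to 99.6.
- Two stops: 6/8 = 75.0%; Beta(6, 3) and Beta(7, 2). CI 34.9 to 96.8.
- Three stops: 6/9 = 66.7%. CI 29.9 to 92.5.
- If a stopped subject is not replaced: 5/5 = 100% (47.8 to 100) becomes 5/6 = 83.3% (35.9 to 99.6).

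For safety, assume one fiducial-phase event that stops the procedure and no other event. The current set gives 0/6 = 0%, upper limit 1 − 0.025^(1/6) = 45.9%. A set that starts at the endoscopy gives 1/7 = 14.3% (0.4 to 57.9).

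**The case against.** Sets defined by attempted treatment are common in device studies, and much of the plan already limits the damage. Three stronger readings are tempting, and the documents do not support them.

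- *Fiducial-phase events vanish from safety reporting.* They do not. Protocol 7.7 records and lists all events from fiducial placement. SAP 3.4.1 names no population for its summary tables, so exclusion from those tables is an inference. What is lost is membership of the set that percentages would normally use.
- *Every failure to reach the target leaves the denominator.* It does not. A needle that crosses the duodenum but misses the space, or delivers no gel, leaves the subject in ITT as a failure. Only stops before that point drop out.
- *Calling subjects treated shrinks the denominator further.* SAP 3.1 fixes the denominator as ITT, and SAP 3.1.3 itself says ITT. The phrase is loose wording.

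Other objections stand in part. Non-injection subjects and their reasons are reported in disposition, and SAP 5.1.4 tabulates access difficulties. SAP 5.1.1 pairs not attempted with stopping before the index procedure, which could be read as treating a subject stopped during the procedure as attempted; Protocol 6.4.2 says otherwise, and the two need reconciling. The No TraceIT population could hold some of these subjects, but no analysis is assigned to it. Some pre-needle stops are eligibility failures: inclusion criterion 3 may be judged at the fiducial EUS, and exclusion criterion 3 covers abnormalities that block access. These should not count against the device. Finally, fiducial risks are listed apart from TraceIT risks, so counting a fiducial complication as a technical failure is a choice of estimand. That argues for showing both rates.

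**Conclusion.** The point holds in this limited form. The stated rule can only favor the primary success rate, and it leaves some collected events outside the Safety Population percentages. One omitted pre-needle stop is the difference between 100% and 85.7%, with the lower limit falling from 54.1% to 42.1%; two give 75.0% and 34.9%.

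These figures rest on assumed counts and on reading the needle as the TraceIT needle. If no subject is stopped before needle insertion, nothing changes. No stated figure is wrong. The study has no hypothesis or success threshold, so no decision rule is overturned, and the intervals overlap widely. It is still worth correcting, because the set is so small and the correction is cheap.

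**What to change.** 1. Define the Safety Population as all enrolled subjects in whom the index endoscopy (fiducial and TraceIT procedure) is started. Name it as the population for the SAP 3.4.1 tables, and delete the statement that Safety equals ITT (Protocol 7.3.5, SAP 4.1.5).
2. Keep the attempted-injection ITT rate. Beside it, report Technical Success among eligible subjects in whom the index procedure was started with intent to inject, counting no access or no injection as failure. Show separately those found ineligible at that EUS, such as subjects with duodenal invasion, whom Protocol 7.5 already calls secondary screening failures.
3. Reconcile the non-injection and not-attempted wording in Protocol 6.4.2, 6.4.5.1 and 6.4.7 and SAP 5.1.1. In Protocol 7.6.2 and SAP 3.1.3, replace the reference to treated subjects with the ITT wording of SAP 3.1.

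**Cost.** Wording and one extra row of output. SAP 5.1.4 already plans to capture EUS, fiducial and needle times. Thirty-day follow-up of pre-needle stops is assured only under the broader definition in Protocol 6.4.7, which is another reason for item 3. The reported success rate may be less favorable. A wider Safety set would also dilute the percentage with an RT delay caused by TraceIT administration, because subjects never attempted cannot have that event; show that percentage among attempted subjects as well.

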6.4.3 Informed Consent

All subjects considered for enrollment in the study must complete an IRB approved informed consent PRIOR to any study-specific procedures being performed. The Investigator should adhere to GCP and to the ethical principles as delineated in 21 CFR Part 50. Failure to obtain a signed informed consent renders the subject ineligible for the study. Subjects must be willing to undergo transduodenal placement of fiducial markers and the TraceIT Tissue Spacer and must be willing to consent to study procedures and return for follow-up visits upon completion of RT.

6.4.4 Screening/Baseline Assessments (within 45 days prior to planned TraceIT hydrogel injection)

Subjects who appear to meet the eligibility criteria will be consented for the study and will undergo screening. Information to be collected at this visit includes:

- Demographic information: date of birth, weight and height, race
- Disease documentation: tumor location, initial resectability status, tumor staging, largest pre-treatment dimension of tumor (cm)
- Medical/Surgical History/Current status: concomitant medical conditions, prior medical conditions, prior surgeries, prior therapies (e.g., induction chemotherapy)
- Physical Examination: including sitting blood pressure, pulse, temperature, weight, anticoagulation status, Zubrod Performance Score
- Laboratory testing for hematology plus platelets, creatinine, AST/ALT and bilirubin and baseline serum carbohydrate antigen (CA) 19-9
- Pregnancy test for women of child-bearing potential

- EORTC-QLQ-C30 and QLQ-PAN26
- Assessment of baseline duodenal symptoms per NCI CTCAE
- Baseline concomitant medications

6.4.5 Fiducial Placement and TraceIT Tissue Spacer Injection

[figure not shown]
6.4.5.1 Injection

The TraceIT Tissue Spacer is to be injected between the pancreas and the duodenum by the participating study physician using a transduodenal approach and with endoscopic ultrasound (EUS) guidance as depicted in **Figure 2**.

An EUS assessment of the space between the pancreas and the duodenum before and after injection is to be performed. The following information will be collected:

- Ability to access injection site and inject TraceIT material
- Average duodenal space measurements on CT measured at 3 points along the head of the pancreas
- TraceIT Injection Procedure Duration
- Ease of Device Use
- Device malfunctions
- Adverse Events per NCI CTCAE ver. 4.0

Figure 2: TraceIT Tissue Spacer Injection into Periduodenal Space using Endoscopic Ultrasound Guidance (Rao et al, used with permission)

The subject is to be positioned in the left-lateral position and an endoscopic ultrasound (EUS) will be used to identify the duodenum and HOP interface.

Under EUS guidance, the 19 or 22G fine needle aspiration (FNA) needle will be guided through the EUS scope and into the potential space between the duodenum and pancreas. The TraceIT Tissue Spacer will be prepared per the supplied IFU. Once the needle has been confirmed to be in

the proper position, the TraceIT hydrogel will be injected in 1mL increments. This process will then be repeated as the needle is repositioned around the target region, injecting TraceIT hydrogel at each location to a total volume of up to 20 mL hydrogel (40 mL of diluted TraceIT hydrogel in a 1:1 ratio).

- Note: If the needle is inserted through the duodenum, but the TraceIT Tissue Spacer is not injected, the subject will be followed for 30 days and included in the safety analysis. No further imaging is required for these “non-injection” subjects.

Following injection of the TraceIT hydrogel, the needle is to be removed, EUS images are to be acquired and measurements obtained as described above.

The lot number of the TraceIT Tissue Spacer device(s) used, the number and timing of applications is to be recorded on the TraceIT Tissue Spacer Injection CRF.

The subject should be assessed for adverse events during the follow-up period following the TraceIT Tissue Spacer injection.

6.4.5.2 Post-Injection CT Scan Acquisition

Following the TraceIT hydrogel injection, each subject is to undergo a repeat planning simulation scan to obtain a second RT radiation computer treatment plan with the TraceIT Tissue Spacer *in situ*.

The first and second RT treatment plans (pre- and post-TraceIT Tissue Spacer injection) will be compared to evaluate the displacing properties of the TraceIT Tissue Spacer.

